10.2.1.1 Consultation with Medical Monitor and local hepatologist

Potential drug-induced liver injury events require notification of the Medical Monitor within 24 hours (eg, by laboratory alert), and the subject must be discussed with the Medical Monitor as soon as possible. If required, the subject must also be discussed with the local hepatologist. The local hepatologist is the expert usually consulted by the treating physician for assessment and management of potential hepatic disease. This would usually be a hepatologist, but may be a gastroenterologist. If determined necessary, this discussion should be followed by a full hepatology assessment (see Section 10.2.1.3) and SAE report (if applicable).

10.2.1.2 Immediate action: determination of IMP discontinuation

All PDILI events require immediate action, testing, and monitoring.

The immediate action is dependent on the laboratory values and symptoms of hepatitis or hypersensitivity and ranges from continuation of IMP (followed by immediate investigation) to immediate and permanent discontinuation (see Section 6.4.1 and Table 10-3 for details).

When IMP is discontinued, all concomitant medications and herbal supplements that are not medically necessary should also be discontinued. The investigator should also consider dose reduction for medically necessary concomitant medication and consider changing any medically required concomitant medication known to be hepatotoxic to a suitable alternative.

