10.2.1 Evaluation of PDILI

The PDILI IMP discontinuation criteria for this study are provided in Section 6.4.1, with the accompanying required follow-up investigation and monitoring detailed below. All PDILI events must be reported as an AE and reported to the study site and sponsor within 24 hours of learning of their occurrence. Any PDILI event that meets the criterion for potential Hy’s Law must be reported as an AE of special interest (see Section 10.1.1.3), and, if applicable, also reported as an SAE (see Section 10.1.1.2).

Evaluation of PDILI consists of the diagnostic testing and continued monitoring included in Table 10-3 (specific tests dependent on laboratory results and corresponding symptoms) and consultation with a local hepatologist (if applicable; discussed in Section 10.2.1.1). The local hepatologist is the expert usually consulted by the treating physician for assessment and management of potential hepatic disease. This would usually be a hepatologist, but may be a gastroenterologist. Additional investigation and monitoring may be required and adapted based on the diagnosis after the cause of the liver injury/abnormality is confirmed (details in Section 10.2.1.4).

The results of all monitoring, including laboratory testing and other testing, should be made available to the study site and sponsor.

All initial tests resulting in abnormal hepatic laboratory values need to be repeated, but appropriate medical action must not be delayed waiting for the repeat result.

If tests are done locally for more rapid results, a concurrent sample should also be sent to the central laboratory whenever possible. Medical care decisions are to be made initially using the most rapidly available results and a conservative approach must be taken if the results from the 2 laboratory tests are significantly different. Data from the local and central laboratory are to be recorded on the applicable eCRF pages.

When IMP is discontinued, all concomitant medications and herbal supplements that are not medically necessary should also be discontinued. In these cases, the investigator should also consider dose reduction for medically necessary concomitant medication and consider changing any medically required concomitant medication known to be hepatotoxic to a suitable alternative.

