When IMP is stopped due to PDILI (as described in Section 6.4.1), IMP must be permanently discontinued. Rechallenge with a substance potentially causing drug-induced liver injury is dangerous, may be fatal, and must not occur.

The table below summarizes the approach to investigate PDILI.

This document cannot be used to support any marketing authorization application and any extensions or variations thereof.

REDACTED COPY

Table 10-3: Required investigations and follow up for PDILI

| Laboratory value | | Immediate | | | Follow up | |
|--------------------------------------|---------------------|--|---|---|---|---|
| ALT or AST | Total bilirubin | Symptoms ^a of hepatitis or hypersensitivity | Consultation requirements | Actions | Testing | Evaluation |
| ≥3xULN | ≥2xULN ^b | NA | Hepatology consult. ^c Medical Monitor must be notified within 24 hours (eg, by laboratory alert) and subject discussed with Medical Monitor ASAP. | Immediate, permanent IMP discontinuation. | Essential: Must have repeat liver chemistry values and additional testing completed ASAP (see Section 10.2.1.3); recommended to occur at the site with HCP. | Monitoring of liver chemistry values at least twice per week until values normalize, stabilize, or return to within Baseline values. ^d |
| ≥8xULN | NA | NA | | | | |
| ≥3xULN | NA | Yes | | | | |
| ≥3xULN (and ≥2x Baseline) and <5xULN | <2xULN | No | Discussion with Medical Monitor required if the criterion that allows for IMP continuation is met. | Further investigation of immediate IMP discontinuation not required (see Section 10.2.1.2). | Not required unless otherwise medically indicated (at discretion of investigator). | |
| ≥5xULN (and ≥2x Baseline) | <2xULN | No | Discussion with Medical Monitor required. | Immediate, permanent IMP discontinuation. | Essential: Every attempt must be made to have repeat liver chemistry values and additional testing completed within 48 hours at the site with HCP (see Section 10.2.1.3). | Monitoring of liver chemistry values at least twice per week until values normalize, stabilize, or return to within Baseline values. ^d |

ALP=alkaline phosphatase; ALT=alanine aminotransferase; ASAP=as soon as possible; AST=aspartate aminotransferase; HCP=healthcare practitioner;

IMP=investigational medicinal product; NA=not applicable; PDILI=potential drug-induced liver injury; ULN=upper limit of normal

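### For the one liver-signal group that may stay on study drug, Table 10-3 calls testing not required, while Sections 10.2.1 and 10.2.1.2 require a repeat test and immediate testing

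*Protocol*

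**What the plan says.** **Who may continue.** Protocol Section 6.4.1 lists the liver criteria that force permanent discontinuation and a single criterion under which the investigator may keep the subject on drug: ALT or AST from 3xULN to below 5xULN (and at least twice Baseline), total bilirubin below 2xULN, and no eosinophilia, fever, rash or hepatitis symptoms. It then requires the Section 10.2.1 evaluation to be started, without exempting this group.

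**The running text.** Section 10.2.1.2 states "All PDILI events require immediate action, testing, and monitoring". It describes the range of actions as one that "ranges from continuation of IMP (followed by immediate investigation) to immediate and permanent discontinuation", so subjects who continue are expressly included. Section 10.2.1 states "All initial tests resulting in abnormal hepatic laboratory values need to be repeated". It also says that the evaluation follows Table 10-3, with "specific tests dependent on laboratory results and corresponding symptoms".

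**The table.** In the Table 10-3 row for the group that may continue, the consultation cell reads "Discussion with Medical Monitor required if the criterion that allows for IMP continuation is met" and the Testing cell reads "Not required unless otherwise medically indicated (at discretion of investigator". The other two filled Testing cells read differently. The first row has "Must have repeat liver chemistry values and additional testing completed ASAP". The row for at least 5xULN has "Every attempt must be made to have repeat liver chemistry values and additional testing completed within 48 hours at the site with HCP".

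**Related sections.** Section 10.2.1.1 requires the Medical Monitor to be notified within 24 hours and makes a full hepatology assessment conditional on need. Section 10.2.1.3 ties the aetiology work-up (Tables 10-4 and 10-5) to a reasonable possibility that the study drug was the cause. Section 10.2.1.4 requires monitoring until values normalise, stabilise or return to Baseline.

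**The concern.** This is the only PDILI group still exposed to the suspect drug. Under Section 6.4.1, a rise to 5xULN, bilirubin of at least 2xULN, or new symptoms would force permanent discontinuation. The repeat value therefore bears directly on whether dosing may go on. Section 10.2.1 presents Table 10-3 as the summary of the approach, so a site may well act on the cell alone. A site doing that could skip or delay a repeat test that the running text requires.

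**Working it through.** No arithmetic is involved and the plan gives no figure to reproduce. The check sets the instructions side by side for the group with ALT or AST from 3xULN to below 5xULN, bilirubin below 2xULN and no symptoms.

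| Place | Repeat liver chemistry | Additional (aetiology) testing | Time |
|---|---|---|---|
| Section 10.2.1 | Required for every abnormal initial result | As set out in Table 10-3 | None stated |
| Section 10.2.1.2 | Within the testing required for all PDILI events | Investigation follows continuation | Immediate |
| Section 10.2.1.1 | Not addressed | Full assessment if found necessary | Medical Monitor notified within 24 hours |
| Section 10.2.1.3 | Not addressed | When the drug is a reasonable suspect | None stated |
| Table 10-3, Testing cell | Not required unless medically indicated | Not required unless medically indicated | None stated |

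**Step 1: does the cell cover repeat chemistry?** Table 10-3 has 5 rows. As extracted, 3 Testing cells are filled; the blanks in the second and third rows are taken as merged with the first. Of those 3, 2 name repeat liver chemistry together with additional testing and give a time (as soon as possible; 48 hours). The third is the cell in question. In a column whose other entries include repeat chemistry, an unqualified statement that testing is not required reads as covering repeat chemistry too.

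**Step 2: does this contradict the running text?** Yes, on two points. Section 10.2.1 requires the repeat with no exception by group. Section 10.2.1.2 requires immediate testing for all events and names continuation of study drug explicitly.

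**Step 3: does it also contradict the work-up rules?** No. Sections 10.2.1.1 and 10.2.1.3 both make the aetiology work-up a case-by-case matter. A reasonable suspicion of the study drug fits within medically indicated. The conflict is therefore one conflict between two rules, on repeat chemistry and immediate testing.

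**Step 4: would scheduled sampling supply a prompt repeat?** Not reliably. In Section 8.2.3, chemistry is listed at Weeks 6, 12, 20 and 24 but not at Weeks 8 or 16. After a Week 12 signal, the next scheduled chemistry is 20 - 12 = 8 weeks later.

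**Step 5: is it an extraction fault?** Probably not. The cell is a complete, intelligible statement. The Actions cell in the same row may be garbled and the Evaluation cell is blank, so neither is relied on here.

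**The case against.** The strongest reply is that the running text defers to the table. Section 10.2.1 makes the specific tests depend on results and symptoms, Section 10.2.1.2 points to Table 10-3 for details, and a specific row normally refines a general sentence. Section 10.2.1.3, which both other filled Testing cells cite, uses the word testing in its heading for the search for an alternative aetiology. On that view the cell says only that the aetiology work-up is not automatic, and the repeat test remains governed by Section 10.2.1. The Actions cell of the same row, if its text is damaged, may originally have ordered further investigation and so agreed with Section 10.2.1.2.

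Part of this stands. The work-up provisions can be reconciled with the cell, and the repeat test is still required by Section 10.2.1 for anyone who reads that section. What does not stand is the claim that the cell is clear. It sits in a column that elsewhere includes repeat chemistry, it does not limit itself to the work-up, and Section 10.2.1.2 makes no exception. If only the work-up was meant, the cell should say so. A reading of the Actions cell that depends on reconstructing its text cannot settle the matter.

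Three stronger inferences are tempting and are not supported. A reader might infer that these subjects go unmonitored, but Medical Monitor contact (Section 10.2.1.1) and follow-up monitoring (Section 10.2.1.4) still apply. A reader might infer that the aetiology work-up is lost, but Section 10.2.1.3 still requires it when the drug is a reasonable suspect. A reader might count three incompatible testing rules, but Step 3 of the working shows that the work-up rules fit together.

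**Conclusion.** The conflict is real and of low magnitude. The Testing cell for the single group that may continue study drug cannot be squared, as written, with the requirement to repeat abnormal liver tests and to test immediately. It affects 1 of 5 rows of Table 10-3. The number of subjects cannot be derived from the protocol and is probably small. The harm is limited to contradictory site instructions, with no time stated in that row, for a subject still on drug. Nothing here touches the endpoints, the type I error or the power.

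The conclusion rests on two assumptions: that the Testing cell is printed as extracted, and that the Testing column means the same thing in every row. If the sponsor intended the cell to cover the aetiology work-up only, the remedy is the same, because the cell needs to say so.

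**What to change.** Replace the Testing cell of the row for 3xULN to below 5xULN in Table 10-3 with: *Repeat liver chemistry as soon as possible, within a limit set by the sponsor (Section 10.2.1). Additional testing per Section 10.2.1.3 when there is a reasonable possibility that the IMP was the cause, or when otherwise medically indicated.*

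The protocol sets no time for this group, so the limit is the sponsor's to choose. The 48 hours in the row for at least 5xULN is one possible model.

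In Section 10.2.1.2, keep the requirement for immediate action, testing and monitoring as it stands. Add only: *The extent of additional testing is as stated in Table 10-3 and Section 10.2.1.3.* This avoids weakening the general rule and does not impose the full Table 10-4 panel on every asymptomatic elevation.

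The cost is one table cell and one added sentence in an amendment. In practice it means a few extra blood samples, and possibly an unscheduled visit, in rare subjects.

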10.2.1.3 Testing: identification/exclusion of alternative etiology

The measurements and additional information required for the assessment of PDILI events when there is a reasonable possibility that they may have been caused by the IMP are detailed in Table 10-4 (laboratory measurements) and Table 10-5 (additional information). Results of the laboratory measurements and information collected are to be submitted to the sponsor on the corresponding eCRF. If the medical history of the subject indicates a requirement for other assessments not included below, these additional assessments should be completed and submitted, as applicable.

All blood samples should be stored, if possible. If tests are done locally for more rapid results, a concurrent sample must also be sent to the central laboratory.

The following measurements are to be assessed:

Table 10–4: PDILI laboratory measurements

| | |
|-------------------------|--|
| Virology-related | Hepatitis A IgM antibody |
| | HBsAg |
| | Hepatitis E IgM antibody |
| | HBcAb-IgM |
| | Hepatitis C RNA |
| | Cytomegalovirus IgM antibody |
| | Epstein-Barr viral capsid antigen IgM antibody (if unavailable, obtain heterophile antibody or monospot testing) |
| Immunology | Anti-nuclear antibody (qualitative and quantitative) |
| | Anti-smooth muscle antibody (qualitative and quantitative) |
| | Type 1 anti-liver kidney microsomal antibodies (qualitative and quantitative) |
| Hematology | Eosinophil count |
| Urinalysis | Toxicology screen |
| Chemistry | Amylase |
| | If total bilirubin $\geq 1.5 \times \text{ULN}$, obtain fractionated bilirubin to obtain % direct bilirubin |
| | Serum CPK and LDH to evaluate possible muscle injury causing transaminase elevation |
| Additional | Prothrombin time/INR ^a |
| | Serum pregnancy test |
| | PK sample |

ALT=alanine aminotransferase; CPK=creatine phosphokinase; HBcAb-IgM=hepatitis B core antibody-IgM; HBsAg=hepatitis B surface antigen; IgM=immunoglobulin M; INR=international normalized ratio; LDH=lactate dehydrogenase; PDILI=potential drug-induced liver injury; PK=pharmacokinetic; RNA=ribonucleic acid; ULN=upper limit of normal

^a Measured only for subjects with ALT $> 8 \times \text{ULN}$, elevations in total bilirubin, and symptoms of hepatitis or hypersensitivity. Hepatitis symptoms include fatigue, nausea, vomiting, and right upper quadrant pain or tenderness; hypersensitivity symptoms include eosinophilia ($> 5\%$), rash, and fever (without clear alternative cause).

The following additional information is to be collected:

Table 10–5: PDILI information to be collected

| |
|--|
| New or updated information |
| Concomitant prescription and over-the-counter medications (eg, acetaminophen, herbal remedies, vitamins); dosages and dates should be included. |
| Pertinent medical history, including the following: 
 • History of liver disease (eg, autoimmune hepatitis, nonalcoholic steatohepatitis or other “fatty liver disease”) • Adverse reactions to drugs • Allergies • Relevant family history or inheritable disorders (eg, Gilbert’s syndrome, alpha-1 antitrypsin deficiency) • Recent travel • Progression of malignancy involving the liver (Note: Metastatic disease to the liver, by itself, should not be used as an explanation for significant AST and/or ALT elevations.) |
| The appearance or worsening of clinical symptoms of hepatitis or hypersensitivity (eg, fatigue, nausea, vomiting, right upper quadrant pain or tenderness, decreased appetite, abdominal pain, jaundice, fever, or rash) |
| Recent clinically significant hypotension or hypoxemia with compromised cardiopulmonary function |
| Alcohol and illicit drug use |
| Results of liver imaging or liver biopsy, if done |
| Results of any specialist or hepatology consult, if done |
| Any postmortem/pathology reports |

ALT=alanine aminotransferase; AST=aspartate aminotransferase; PDILI=potential drug-induced liver injury

10.2.1.4 Follow-up evaluation

Potential drug-induced liver injury events require follow-up monitoring as described in [Table 10-3](#).

Monitoring should continue until liver chemistry values normalize, stabilize, or return to Baseline. Determination of stabilization is at the discretion of the investigator in consultation with the hepatologist (as applicable) and UCB responsible physician, as needed.

10.2.2 Pregnancy testing

Females of childbearing potential (who have not been surgically sterilized or who are not at least 2 years postmenopausal) will have serum and urine dipstick pregnancy testing performed according to the schedule of study assessments in [Table 5–1](#), [Table 5–2](#), and [Table 5–3](#).

10.3 Other safety measurements

10.3.1 12-lead ECG

Standard 12-lead ECGs will be performed according to the schedule of study assessments in [Table 5–1](#), [Table 5–2](#), and [Table 5–3](#).

The ECG recordings should be performed at the same time of day (when possible) and prior to blood sample collection and vital sign assessments. Care should be taken to assure proper lead placement and quality ECG recordings. If possible, subjects should rest in a supine position at least 5 minutes prior to each recording and should be motionless during the recording. In pediatric subjects (<18 years of age), 12-lead ECGs (2 interpretable recordings) approximately 20 to 30 minutes apart must be performed.

10.3.1.1 Overall ECG interpretation

Electrocardiograms will be reviewed locally by the investigator, subinvestigator, or qualified designated reader. If the reading identifies a second- or third-degree AV block or another abnormal ECG finding that is assessed by the investigator to be clinically significant, then the ECG should be repeated on the same day. If the clinically significant abnormality is confirmed by the repeat ECG, then the subject must be withdrawn from the study (see Section 6.4). The investigator may consult with a cardiologist to confirm the presence of a clinically significant ECG abnormality. It remains the responsibility of the investigator to decide whether an ECG finding is of clinical significance on the basis of the complete clinical picture and whether this finding influences the subject's participation in the study.

10.3.2 Vital signs, body weight, and height

Noninvasive BP (systolic and diastolic) and pulse rate will be measured at clinic visits in a supine position after at least 3 minutes at rest, according to the schedule of study assessments in Table 5-1, Table 5-2, and Table 5-3. Assessment of orthostatic changes will be as follows: after the 3-minute measurement in a supine position, the subject is asked to stand and BP and pulse rate are taken approximately 1 minute and approximately 3 minutes after the subject stands up, as feasible. Blood pressure measurements should be taken with the proper placement and proper sized cuff to obtain accurate measurements.

Body weight will be determined without shoes and wearing light clothing and height will be measured without shoes. Body weight and height will be measured using equipment that is age appropriate and assessed according to the tabular schedule of study assessments (Table 5-1, Table 5-2, and Table 5-3).

10.3.3 New seizure types

Incidence of new seizure types, and increase in absence seizure days per 28 days or myoclonic seizure days per 28 days during the Treatment Period will be assessed using the seizure count information recorded on the subject diaries (see Section 9.3.1).

10.3.4 Physical examination

Physical examinations will be performed by a medically qualified clinician licensed to perform the examination, according to the schedule of study assessments in Table 5-1, Table 5-2, and Table 5-3. Clinically significant physical examination findings are to be reported as AEs.

10.3.4.1 Complete physical examination

The complete physical examination will include cardiac and respiratory function via auscultation and review of all body systems.

10.3.4.2 Brief physical examination

The brief physical examination will include review of the following body systems:

- Cardiovascular
- Pulmonary
- Abdominal (hepato-gastrointestinal)
- Dermatologic

10.3.5 Tanner Stage

At Visit 2 and Visit 10/ET Visit, the investigator or qualified designee will evaluate the subject's sexual development using the 3-item Tanner scale, according to the tabular schedules of study procedures (Section 5.2). The investigator should use clinical judgment in deciding which subjects are selected for evaluation of Tanner Stage (ie, those subjects who are pubescent at Visit 2 or who will enter puberty during the course of the study).

10.3.6 Neurological examination

Neurological examinations will be performed by a medically qualified clinician with documented training in the conduct of neurological examinations, according to the schedule of study assessments in Table 5-1, Table 5-2, and Table 5-3. If possible, the same clinician should conduct all neurological examinations for the same subject during the study. The investigator or subinvestigator is responsible for confirming the diagnosis of IGE with PGTC seizures.

